#### **Laboratory values and ECG results:**

- Only when judged as clinically significant (i.e., some measures or interventions are required, the change is outside of normal physiological variation range as judged by the investigator), the change of laboratory values or ECG parameters can be regarded as AEs. Repeated laboratory test and/or continuous monitoring of abnormal values are not regarded as intervention. Moreover, repeated or additional non-invasive examination performed to verify, evaluate or monitor abnormality is not regarded as intervention.
- If abnormal laboratory findings or ECG findings are pathological results of an overall diagnosis (e.g., creatinine increased in renal failure), only the diagnosis should be reported as AE accordingly.

# **Pre-existing diseases:**

• Pre-existing conditions should not be recorded as AEs. However, if these concomitant conditions worsen or have complications, such worsening or complications should be recorded as AEs (after administration of the study drug) accordingly.

#### **Change in severity of AE:**

• If the patient experiences any changes in severity of AEs: (1) when the CTCAE grade is elevated, the AEs should be recorded separately, and the start date of the grade-elevated AE should be the same as the end date of the original AE; (2) when the CTCAE grade is reduced, the AE is not recorded separately, with only the highest CTCAE grade recorded, and the actions taken with the study drug and causal relationship with the study drug all remained as the records of the highest CTCAE grade, but the relevant information should

be updated in a timely manner, especially the outcomes and the end date.

#### **Surgeries or procedures:**

• Surgeries during the study period should be considered as AEs, but operations/therapies such as abdominocentesis and thoracocentesis should not be recorded as AEs.

# 8.1.2 Collection and reporting process of AEs

#### **AE** collection period

AEs will be collected from the first dose of investigational product to 28 days after the last dose of investigational product or the start of new anti-tumor therapy (whichever occurs first). During the AE collection period, all AEs should be reported in the source medical record and the eCRF. After the AE collection period, only the existing AEs, newly occurred AEs definitely related/possibly related/possibly unrelated to the study drug/ucertain, and AEs leading to death will be recorded. For AEs still existing after the end of study treatment, if they are related to the study treatment, they will all be followed up until resolution, stabilization, death, loss to follow-up or it is reasonably explained.

All adverse medical events that occur during the period from subject's signing of the ICF to the first dose of the investigational product will be recorded as medical history instead of being recorded as AEs, unless they meet one of the following conditions:

- Any adverse medical event related to procedures specified in the clinical study protocol (e.g., bruising caused by blood sampling for laboratory test, etc.);
- Adverse medical events caused by treatment discontinuation related to clinical study protocol (e.g., change or discontinuation of prior concomitant medications).

#### **AE** reporting

At each study visit, the investigator will assess whether there is a subjective AE. A neutral question can be asked, such as "How do you feel since the last visit?".

All clinically significant laboratory abnormalities confirmed by repeated laboratory test will be followed-up until these abnormalities are resolved to acceptable level or satisfactory explanation is given.

For all AEs, no matter stated by the subject, asked out by the investigator or found out by physical examination, laboratory test or other methods, they should all be recorded in the source medical records and the eCRF completely no matter regardless of being related to the study drug as considered by the investigator. The following information will be recorded for AEs:

Event term.

- Start and end date.
- Severity.
- The investigator's judgment on the causal relationship between the AE and the study drug.
- Relevant actions taken with the study drug.
- Treatment or interventional measures taken for AEs.
- Event outcome.
- SAE or not.

# **8.1.3** Evaluation of severity

The investigator should grade AEs according to CTCAE v5.0. Note: CTCAE v5.0 is only used for grading of AEs, and it is not used to determine whether the AE is an SAE.

Referring to CTCAE v5.0, if there are AEs not listed in the table, they can be classified into 1-5 grades according to the following criteria:

Grade 1: mild; asymptomatic or mild symptoms; clinical or diagnostic observations only; intervention not indicated.

Grade 2: moderate; minimal, local or noninvasive intervention indicated; limiting age-appropriate instrumental ADL (instrumental ADLs refer to preparing meals, shopping for clothes, using the telephone, managing money, etc.).

Grade 3: severe or medically significant but not immediately life-threatening; hospitalization or prolongation of hospitalization indicated; disabling, limiting self-care ADL (self-care ADL refers to bathing, dressing and undressing, feeding self, using the toilet, taking medications, and not bedridden).

Grade 4: life-threatening; urgent intervention indicated.

Grade 5: death related to AEs.

#### 8.1.4 Evaluation of causal relationship

The causal relationship of AEs with the study drug is evaluated as definitely related, possibly related, possibly unrelated, definitely unrelated and uncertain (see Table 3).

Table 3 Criteria for evaluation of causal relationship between AE and study drug

Causal relationship	Temporal sequence	Known reaction type	Influence of other confounding factors
Definitely	There is a rational temporal	The event meets the	Influence of other confounding
related	relationship between the	known reaction type	factors such as pre-existing
	AE's occurrence and	of study drug.	diseases has been excluded.

Causal relationship	Temporal sequence	Known reaction type	Influence of other confounding factors
	administration. For example, the AE will disappear, be relieved or improved rapidly after drug withdrawal, which may recur even aggravate obviously after resuming the drug (that is, rechallenge positive).		
Possibly related	The event follows a temporal sequence from the drug's administration.	The event meets the known reaction type of study drug.	The patient's clinical status or other therapies may also give rise to such event.
Possibly unrelated	The event does not follow a temporal sequence from the drug's administration.	The event does not quite meet the known reaction type of study drug.	The patient's clinical status or other therapies may also give rise to such event.  Relationship with administration cannot be ruled out.
Definitely unrelated	The time of the event does not follow a temporal sequence from the drug's administration.	The event meets the known reaction type of non-study drug.	The patient's clinical status or other therapies may also give rise to such event. The event disappears after the disease status improves or other treatments are stopped, but the event reoccurs after repeated use of other treatments. It is closely related to other risk factors.
Uncertain	The occurrence time of the event has no clear relationship with the temporal sequence of medication.	The event is similar to the known reaction type of the study drug.	Use of other drugs may also cause such event.  There is no enough evidence for judgment.

**Abbreviation:** AE=adverse event.

# 8.1.5 Study drug-related actions

- **Drug withdrawal:** the study drug is withdrawn due to a specific AE.
- **Dose unchanged:** study drug does not need to be withdrawn for a specific AE.
- **Dose reduction:** dose reduction due to a specific AE.
- **Dose interruption:** temporary interruption/suspension of the study drug (including the subject's active interruption of the drug) due to a specific AE, and then resume the drug afterwards.
- **Unknown:** only used when the action taken cannot be determined.

• **Not applicable:** the study drug is withdrawn due to reasons other than specific AEs, e.g., the study has been terminated, the patient died, the study drug has already been stopped before the onset of the AE.

#### 8.1.6 Outcome of AEs

Outcome of AEs can be described as follows:

- **Recovered/resolved, with no sequelae:** the event has been resolved and the patient has no sequelae. "End date of (serious) adverse events" should be indicated.
- Recovered/resolved, with sequelae: the event has been resolved, but the patient has long-term or lifelong sequelae, like hemiplegia caused by stroke. "End date of (serious) adverse events" should be indicated.
- **Recovering/resolving:** the event is not completely resolved, but the patient is recovering. Follow-up visits are required.
- Unrecovered/unresolve: the event is ongoing. Follow-up visits are required.
- **Fatal:** death date should be indicated.
- Unknown: the investigator cannot learn about the AE, e.g., the patient is lost to follow-up.

If outcome of an AE is determined to be "recovering/resolving" or "unrecovered/unresolved" or "unknown", the end date of the AE may not be recorded temporarily.

#### **8.2** ADR

ADR refers to any harmful or undesirable reactions that may occur in clinical trials and be related to investigational products. There is at least a reasonable possibility of a causal relationship between the investigational product and the AE, i.e., the correlation cannot be ruled out.

In this trial, ADRs include AEs that have the causal relationship with the study drug as definitely related, possibly related, possibly unrelated, and uncertain.

#### 8.3 **SAE**

#### 8.3.1 Definition of SAE

SAEs refer to the following medical adverse events occurring after the subject receiving the investigational product:

- Deatha
- Being life-threateningb
- Hospitalization or prolonged hospitalizationc

- Persistent or serious disability or incapacityd
- Congenital abnormalities or birth defecte
- Other important medical eventsf

# Further explanations for SAEs are as follows:

- a. Any death occurring during the study period or within 28 days after the last dose, including those completely unrelated to the study drug. If the patient dies during the study period and an autopsy is conducted, the investigator should provide the sponsor and the Ethics Committee with other necessary information, such as autopsy report and final medical report.
- b. Occurrence of AEs causes immediate risk of death for the patient. These do not include AEs that may cause death after serious progression, e.g., drug induced hepatitis without liver failure.
- c. Any AEs resulting in hospitalization or prolongation of existing hospitalization (prolongation of existing hospitalization means the planned or expected discharge is delayed, usually after staying overnight in the hospital for at least one day). These do not include elective surgeries or examination before admission decided before the study, with no change of treatment course during the study.
- d. Any AEs causing injury, damage or destruction of patient's function and/or physiological structure, physical activity or quality of life.
- e. It is suspected that exposure of parent to the study drug may cause adverse outcome of descendants.
- f. Medical and scientific judgment must be exercised in deciding whether expedited reporting is appropriate in other situations, such as important medical events that may not be immediately life-threatening or result in death or hospitalization but may be considered serious if medical intervention is necessary to prevent one of the above situations. For example, intensive therapy in the emergency room or allergic bronchospasm at home, blood dyscrasia or convulsion not resulting in inpatient hospitalization, or those leading to drug dependence or drug abuse.

#### Death

All death events that occur during administration period or within 28 days after the last dose must be reported to the sponsor/CRO's safety department within 24 hours, and the death causes should be recorded in proper areas in the eCRF and the SAE report. If the death is jointly caused by multiple reasons, the investigator must determine the main cause of the death. The report should include information on AE condition, major or minor causes of death (if any), etc. In case of reports involving death events, the investigator should provide the sponsor/CRO and the Ethics Committee with other necessary information, such as autopsy report and final medical report.

Note: Generally, disease progression (including progressive symptoms and signs) should not be reported as an AE or SAE, but it should be reported as an SAE (with the severity as grade 5) if the patient's death is due to his/her disease progression (and the death can not be included as any of the grade 5 AEs in CTCAE).

#### Hospitalization

AEs requiring hospitalization for treatment are considered as SAEs. In general, hospitalization includes admission and treatment. Hospitalization does not include the followings:

- Rehabilitation facility;
- Nursing home;
- Admission to routine emergency room;
- Surgeries on the same day (e.g., outpatient/same day/ambulatory procedures);
- Unnecessary hospitalization and treatment (e.g., hospitalization for the reason of medical insurance reimbursement).

### 8.3.2 Collection and reporting of SAEs

Except for the SAEs unnecessary to be reported immediately as per the trial protocol or other documents (e.g., Investigator's Brochure), the investigator should report all the SAEs to the Sponsor/CRO in writing immediately, and thereafter provide a detailed and written follow-up report in a timely manner.

For any SAE in the trial, regardless of whether it is related to the study drug or not, the investigator should provide timely rescue treatment, complete the *Serious Adverse Event Reporting Form* within 24 hours of awareness, sign and date it and report it to the sponsor/CRO.

For initial SAE report, the investigator should record in detail about the report source, basic information of the subject, name of the study drug, SAE name, SAE symptoms/vital signs/examination indicators, start and end date, severity, treatment time, actions taken, causal relationship with the study drug and outcomes, etc., and ensure that the record is true, accurate, complete, timely and legal. After the initial report, the SAE should be continuously followed up and relevant new information or updated information of the previous report should be reported in the form of follow-up report timely (the follow-up report should be reported within 24 hours after obtaining the new information).

The investigator must provide causality assessment when reporting SAEs. If the investigator can not confirm whether the AE is an SAE, it will be considered as an SAE before proving its nature.

#### 8.5 Adverse Events of Special Interest (AESIs)

In the expansion trial, AEs meet the DLT definition in Section 4.1.1.4 are considered as AESIs.

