# $\label{lem:decomp} \textbf{DLT evaluation and single-dosing period *:} For the dose escalation trial only.$

Xa: Existing laboratory test results within 48 h are acceptable.

 $X^b$ : Twice in Cycle 2, e.g., D14 and D21 of the cycle, with a time window of  $\pm 3$  days; for Cycles 3 to 5, once at the end of each cycle, with a time window of  $\pm 3$  days; since Cycle 6, once at the end of every 2 cycles, with a time window of  $\pm 3$  days.

 $X^c$ : For Cycle 2-5, once at the end of each cycle, with a time window of  $\pm 3$  days; since Cycle 6, once at the end of every 2 cycles, with a time window of  $\pm 3$  days.

Xd: Existing laboratory test results within the visit time window are acceptable.

In addition to the safety test items specified in the protocol, additional safety test items may be measured as necessary.

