#### 4.1.1.4 DLT Definition

DLT observation period is defined as the period from a single dose to the end of Cycle 1 of multiple-dosing.

DLT is defined as an AE definitely/possibly related to the study drug occurring in the DLT observation period (AEs will be graded according to CTCAE v5.0) which meets any of the following criteria:

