## (3) Other conditions

1) The grade is elevated from baseline with clinically significant and/or unacceptable toxicity, which is judged as a DLT by the SMC.

- 2) Drug discontinuation lasting 7 days or more due to drug-related toxicity.
- 3) The dose received by the subject during the DLT observation period is less than 75% of the scheduled dose due to toxicities attributable to study drug, and the investigator believes that it should be considered as a DLT.

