## 4.1.2 Expansion trial (expansion groups)

Based on the safety, tolerability, PK and efficacy data obtained in previous trials, 1 to 3 appropriate doses (e.g., 100 mg QD, 160 mg QD, and 240 mg QD) will be selected for the expansion trial.

The expansion trial can be initiated when the above doses are demonstrated to have a favorable safety in the dose escalation trial (i.e., the number of subjects experiencing DLT in the group is  $\leq 1/6$  of total subjects of the group), without waiting for the completion of the entire dose escalation trial.

Each expansion group will enroll 12 subjects to investigate the efficacy, safety and PK profiles of BB102 tablets. During the expansion trial, AEs meeting the definition of DLT will be regarded as AEs of special interest for safety assessment, thereby enriching the safety assessment data.

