### 4.3.2 Single-dose phase (for dose escalation trial only)

#### Day 1 (D1):

Specific procedures and assessments are as follows:

Vital signs: Body temperature, blood pressure, heart rate and respiration. For D1, it will be

measured within 1 h pre-dose and at 10 h ( $\pm 1$  h) post-dose on D1. If there are corresponding clinical symptoms at other time, vital signs should also be measured, and the data should be recorded.

- ➤ 12-lead ECG: Measurements will be performed after resting in supine position, and the data (PR, QRS, QT and QTcF) will be recorded. For D1, it will be measured within 1 h pre-dose and at 10 h (±1 h) post-dose on D1. If there are corresponding clinical symptoms at other time, ECG should also be performed, the data should be recorded, and the ECG results should be kept.
- > Study drug administration: See Section 5.2 and Section 6.1 for details.
- **PK blood collection:** See Section 4.4.1 for details.
- **Blood collection for metabolite identification:** See Section 4.4.2 for details.
- ➤ AE: See Section 8 for details.
- > DLT evaluation.
- **Concomitant medications**: see Section 6.2 for details.
- > Inpatient nutrition assessment (NRS-2002): assessed as needed.

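### Expansion AESIs are defined through a DLT window that the expansion does not have, so as written the set is empty or ends with Cycle 1

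*Protocol*

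**What the plan says.** Section 8.5 contains one sentence: "In the expansion trial, AEs meet the DLT definition in Section 4.1.1.4 are considered as AESIs". Section 4.1.2 puts the same rule in the design: "During the expansion trial, AEs meeting the definition of DLT will be regarded as AEs of special interest for safety assessment". It adds that the aim is to enlarge the body of safety data. The synopsis repeats this.

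The definition being borrowed contains a time limit. Section 4.1.1.4 states: "DLT is defined as an AE definitely/possibly related to the study drug occurring in the DLT observation period". The same section fixes the window: "DLT observation period is defined as the period from a single dose to the end of Cycle 1 of multiple-dosing".

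The notes to the flow chart mark both the single-dosing period and the DLT evaluation "For the dose escalation trial only". Sections 4.3.2 and 4.3.3 restrict them in the same way.

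**The concern.** An event category meant for the expansion is defined by a window that belongs to the escalation. The expansion has no starting point for that window, and its treatment runs well past the end point. A related event that meets a listed DLT criterion in Cycle 2 or later falls outside the category. Its label then depends on whether the site or the programmer applies the definition as written, moves the start to C1D1, or ignores the window. At stake are the content and consistency of the AESI category.

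**Working it through.** No figure in the protocol needs reproducing. The check sets the sections side by side and then measures the windows.

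**Is there a window in the expansion?**

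1. Section 8.5 cites Section 4.1.1.4 as a whole. Onset in the window stands in the lead sentence of that definition, next to the requirement that the AE be definitely or possibly related, so it is not an optional extra.
2. The window opens with the single dose. That phase is for the escalation only, so an expansion subject never has the opening event.
3. Section 6.1.2 sets dosing rules for the DLT observation period in the escalation only. It handles the whole expansion dosing period together with the escalation's post-DLT period. The protocol thus treats the expansion as having no DLT observation period.
4. Sections 8.5 and 4.1.2 and the synopsis neither waive the window nor supply another.
5. One criterion refers to the window again. Item 3 of the other conditions in Section 4.1.1.4 reads "The dose received by the subject during the DLT observation period is less than 75% of the scheduled dose". Even if the window is dropped from the lead sentence, this item has no measuring period in the expansion.

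**How much time does each reading cover?**

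Inputs: a cycle is 21 days (Section 5.2); treatment continues until a discontinuation criterion is met (Section 6.1.1); data collection closes 8 weeks, or 8 × 7 = 56 days, after the last subject starts (Section 4.7). Share covered = window days ÷ days from first dose to cut-off, for a subject still on treatment then.

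| Reading | Days covered | Share at 56 days | Share at 84 days (4 cycles, illustration) |
|---|---|---|---|
| Definition as written | 0 | 0% | 0% |
| Window moved to start at C1D1 | 21 | 21/56 = 37.5% | 21/84 = 25% |
| Window ignored | all | 100% | 100% |

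**Can the events be recovered from the planned tables?**

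Section 10.4.4 summarises AEs, ADRs, grade ≥3 AEs and SAEs by system organ class, preferred term and grade. Several DLT criteria depend on something else: grade 4 neutropenia lasting more than 3 days, grade 3 toxicity that does not recover within 7 days of supportive treatment, drug stopped for 7 days or more, and the 75% dose criterion. Relatedness differs too. Section 8.2 counts possibly unrelated and uncertain events as ADRs, whereas the DLT definition takes only definitely or possibly related ones.

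An example is a related grade 2 bilirubin increase in Cycle 2 that interrupts dosing for 10 days. If an interruption counts as stopping the drug, it meets the 7-day criterion. It would appear as a grade 2 AE, but nothing in the planned tables would mark it as DLT-type.

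**The case against.** The strongest reply is that the intent is clear. Section 4.1.2 speaks of events during the expansion trial and gives a purpose. A reading that empties the clause cannot be what was meant, and since the expansion has no DLT observation period, the natural inference is that the toxicity criteria carry over without it. That is plausible. But it requires leaving words out of a definition that Section 8.5 cites in full, and it still leaves the 75% criterion without a period. It therefore supports a clarification.

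The second reply is that little depends on the label. This largely stands. AEs are collected from first dose to 28 days after the last dose or to new anti-tumor therapy (Section 8.1.2), SAEs are reported within 24 hours (Section 8.3.2), and Section 8.5 attaches no reporting or follow-up rule to AESIs. A related grade 4 hepatic event in Cycle 2 would still appear in the AE, ADR and grade ≥3 tables.

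Two stronger conclusions might be inferred, and the document supports neither:

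- **That expansion doses would look better tolerated and the RP2D would be affected.** The protocol specifies no AESI summary and ties no dose decision to AESIs; its RP2D objective rests on the escalation's DLTs and MTD.
- **That the expansion is the only sizeable view of toxicity beyond Cycle 1.** Escalation subjects may also continue past Cycle 1, their groups may grow to 4-12 against 12 per expansion group, and the planned totals are 19-42 for escalation and 12-36 for expansion.

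**Conclusion.** The point holds as a defect of definition. On any reading that keeps the window, expansion AESIs are either none or only those with onset in the first 21 days, which conflicts with the purpose stated in Section 4.1.2. The 37.5% is a ceiling that assumes the window opens at C1D1 and the subject is still on treatment at a cut-off at least 56 days after first dose; for a subject who stops earlier the share is higher. It measures time, not events, because the document gives no basis for the timing of toxicity.

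The consequence is moderate. No safety data are lost and the grade-based tables stand. What is lost is reliable identification of DLT-type events from Cycle 2 on, which those tables cannot fully restore. The correction should be made, but it does not threaten the trial's conclusions.

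**What to change.** In Section 8.5, Section 4.1.2 and the synopsis, replace the bare cross-reference with a statement that expansion AESIs are AEs definitely or possibly related to the study drug that meet the toxicity criteria of Section 4.1.1.4 at any time in the AE collection period, irrespective of the DLT observation period. Relatedness must be written out, because it stands in the lead sentence of 4.1.1.4 and not within the hematologic and non-hematologic criteria; citing those lists alone would bring in unrelated grade 3-4 events.

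In the same places, state the period over which the 75%-of-scheduled-dose criterion is measured in the expansion.

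Splitting AESIs into Cycle 1 and later cycles would allow comparison with the escalation DLTs, but is optional.

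The cost is a short text change in three places. AEs, grades and dosing records are already collected, and no dosing rule changes. The downside is that more events will carry the AESI label.
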